## C.11 Analysis Methods for Secondary Objectives

As indicated below, flat or diffuse prior distributions have been identified for all secondary objective analyses.

### C.11.1 Discrete (Dichotomous) Data: Bayesian Version of a Comparison of Proportions

Given proportions  $p_t$  and  $p_c$  for a dichotomous outcome, let each be assigned a flat Beta(1, 1) prior. Then the posterior distributions for  $p_t$  and  $p_c$  follow Beta( $1+Y_t, 1+N_t-Y_t$ ) and Beta( $1+Y_c, 1+N_c-Y_c$ ) distributions, respectively, where  $Y_t$  and  $Y_c$  represent the number of “successes” and  $N_t$  and  $N_c$  represent the number of “tries” (e.g., subjects) in their respective treatment groups. The distribution of the difference  $p_t - p_c$  can be easily estimated by drawing a large number of observations (e.g., 100,000) from each Beta posterior, and subtracting. The posterior probability  $P(p_t / p_c < \theta \mid \text{data})$  is estimated as the proportion of these observations where the ratio is less than  $\theta$ . Similarly, the posterior probability  $P(p_t - p_c < \delta \mid \text{data})$  is estimated as the proportion of these observations where the difference is less than  $\delta$ . A 95% equal-tail Bayesian credible interval can be calculated from the 2.5th and 97.5th percentiles of the sampled distribution of  $p_t - p_c$  or  $p_t / p_c$ , as appropriate. Credible intervals for  $p_t$  and  $p_c$  can be individually calculated as the 2.5th and 97.5th percentiles from their respective (beta) posterior distributions.

### C.11.2 Discrete (Polytomous) Data: Bayesian Version of a Comparison of Proportions

Given the vectors  $\mathbf{p}_t$  and  $\mathbf{p}_c$  of  $k$ -variate proportions for a polytomous outcome, let each be assigned a flat Dirichlet( $\mathbf{1}$ ) prior. The Dirichlet distribution is the multidimensional analog of the Beta distribution. After observing multinomial count data  $\mathbf{Y}_t$  and  $\mathbf{Y}_c$ , the posterior distributions of  $\mathbf{p}_t$  and  $\mathbf{p}_c$  follow Dirichlet( $\mathbf{1}+\mathbf{Y}_t$ ) and Dirichlet( $\mathbf{1}+\mathbf{Y}_c$ ) distributions, respectively. The distribution of the difference  $\mathbf{p}_t - \mathbf{p}_c$  (or ratio) can be easily estimated by drawing a large number of observations (eg, 100,000) from each Dirichlet posterior, and subtracting (or dividing). The marginal posterior probability  $\Pr(p_t^{(i)} - p_c^{(i)} > \delta \mid \text{data})$  for the  $i^{\text{th}}$  component of  $(\mathbf{p}_t - \mathbf{p}_c)$  is estimated as the proportion of these observations where the difference exceeds  $\delta$ . A 95% Bayesian equal-tail credible interval can be calculated from the 2.5th and 97.5th percentiles of the sampled distribution of  $p_t^{(i)} - p_c^{(i)}$ . Posterior probabilities of ratios are similarly calculated from the sampled distribution of  $p_t^{(i)} / p_c^{(i)}$ .

### C.11.3 Discrete (Dichotomous) Data: Bayesian Comparison of Proportions (with Predictions)

The analysis above under “Bayesian Version of a Comparison of Proportions” applies only to subjects with observed data at the time point of interest (eg, the 24-month visit). A modification is required in order to take into account subjects with partial follow-up, as will be the case if non-inferiority is demonstrated for the primary objective at the interim analysis time point.

The modeling is analogous to the predictions in the Primary Objective. Subjects without outcome data for the time point of interest  $T_0$  will be considered to be in intermediate states that are analogous to those used in the primary objective. If  $T_0 = 24$  months, subjects without 24-month outcome data will be considered to be in one of 26 states (13 for each treatment group). The 13 states are:

- no interim data
- E or P or N at 1 month, no subsequent data
- E or P or N at 6 months, no subsequent data
- E or P or N at 12 months, no subsequent data
- E or P or N at 18 months, no subsequent data

If  $T_0$  is later (eg, 3 years), there is one more set of 3 interim states (E or P or N at 24 months). If the time point of interest is sooner (eg, 12 months), only the first few bullets above (measured at time points prior to  $T_0$ ) would apply.

As with the primary objective analysis, subjects in the "E" state at interim time points can be imputed to be "E" at  $T_0$ , with certainty. For each of the remaining interim states (separately by treatment group), the probability of becoming an "E" at 24 months is modeled via a Beta(1,1) prior distribution which is updated to a Beta(1+X, 1+Y) distribution, based on the number X and Y of subjects who went on from that state to become 24-month "E" and "N" subjects, respectively.

Predicting 2-year outcomes for each of these states, and combining with the data from subjects with known 2-year outcomes, a posterior probability of non-inferiority (or superiority) is calculated; it is based on observed 2-year data and also a predictive model that employs interim outcomes and the relationship between those interim outcomes and their corresponding final outcomes that is learned during the current trial.

Inference proceeds from a sampled version of the posterior distribution of  $[p_t - p_c]$  or  $[p_t / p_c]$ , as appropriate, that incorporates both the observed and predicted values at  $T_0$ . With any one imputation of incomplete data, we draw and store a sample from the posterior distribution  $[p_t - p_c | \text{Observed 2-year data, Imputed 2-year data}]$ . By iterating this process we create a sampled version of the  $[p_t - p_c]$  posterior distribution that accounts for uncertainty in the prediction. The probability of superiority is then estimated by the proportion of these stored values wherein  $p_t > p_c$ . By identifying the 2.5th and 97.5th percentiles of the combined stored samples, a 95% credible interval that accounts for uncertainty in the predicted values is obtained. Analogous techniques are used if the quantity of interest is the ratio  $p_t / p_c$ .

In this analysis, all prior distributions (i.e., those for  $p_t$  and  $p_c$  as well as for all transition probability distributions) are Beta(1,1).

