## C.10 Secondary Endpoints

The following secondary endpoints will be compared between TAVI and SAVR subject cohorts using the appropriate Bayesian version of analysis for comparing proportions and continuous variables as described below:

1. Incidence of Major Adverse Cardiovascular and Cerebrovascular Events (MACCE) at 30 days, 6 months, 12 months, 18 months, 24 months, and annually thereafter up to 5 years. MACCE is defined as a composite of:

- All-cause death
- Myocardial infarction (MI)
- All stroke, and
- Reintervention (defined as any cardiac surgery or percutaneous reintervention catheter procedure that repairs, otherwise alters or adjusts, or replaces a previously implanted valve)

MACCE-incidence estimates will be provided for the two treatment groups at 30 days, 6 months, 12 months, 18 months, 24 months, and annually thereafter up to 5 years. The statistical method will be the Bayesian version of a comparison of proportions (with predictions).

Additionally, incidence of MACCE will be compared at 30 days or hospital discharge, whichever is later. The statistical method will be the Bayesian version of a comparison of proportions

2. The occurrence of individual MACCE components at 30 days, 6 months, 12 months, 18 months, 24 months, and annually thereafter up to 5 years.

MACCE components will be summarized and their incidence estimates provided at 30 days, 6 months, 12 months, 18 months, 24 months, and annually thereafter up to 5 years. The statistical method will be the Bayesian version of a comparison of proportions (with predictions).

3. Major Adverse Events (MAE) and individual components of MAE at 30 days, 6 months, 12 months, 18 months, 24 months, and annually thereafter up to 5 years.

Major adverse event (MAE) includes:

- MACCE
- Acute kidney Injury
- Cardiac tamponade
- Prosthetic valve dysfunction – including moderate or severe aortic regurgitation
- Cardiogenic shock
- Prosthetic valve endocarditis
- Life-threatening, disabling or major bleeding
- Major vascular complication
- Cardiac perforation
- Valve malpositioning

MAE events and individual components of MAE will be summarized and the incidence of MAEs will be provided at 30 days, 6 months, 12 months, 18 months, 24 months, and annually thereafter up to 5 years. The statistical method will be the Bayesian version of a comparison of proportions (with predictions).

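### SAP C.11.3 sets a general time point T0 but ties its prediction rule to 24 months; followed literally, this shifts the 12- and 18-month and the 3- to 5-year incidences

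*Combined protocol and SAP*

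**What the plan says.** All references are to SAP version 6.0, the one based on CIP version 12.0.

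C.10 sends 11 secondary endpoints to the comparison of proportions with predictions (items 1-3, 5-7, 13-15, 19 and 22). The MACCE item shows the usual schedule, which ends at year 5: "MACCE-incidence estimates will be provided for the two treatment groups at 30 days, 6 months, 12 months, 18 months, 24 months, and annually thereafter up".

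C.11.3 opens with a general time point T0 and adapts the list of interim states to it. For an earlier T0 the list is cut to the visits that precede it: "If the time point of interest is sooner (eg, 12 months), only the first few bullets above (measured at time points prior to". For a later one, such as 3 years, "there is one more set of 3 interim states (E or P or N at 24 months"). Subjects already in state E are imputed as E at T0.

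The sentences that carry out the prediction are fixed at 24 months:

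- The transition target: "the probability of becoming an 'E' at 24 months is modeled via a Beta(1,1) prior distribution".
- The updating counts X and Y are subjects "who went on from that state to become 24-month 'E' and 'N' subjects, respectively".
- The combination step: "Predicting 2-year outcomes for each of these states, and combining with the data from subjects with known 2-year outcomes".
- The posterior is conditioned on "Observed 2-year data, Imputed 2-year data".

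In the same closing paragraph, by contrast, the posterior used for inference is tied to T0: it "incorporates both the observed and predicted values at" that time point. No sentence tells the analyst to put T0 in place of 24 months.

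**The concern.** The section gives two incompatible instructions. If the 24-month sentences are programmed as they stand, two things follow.

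- **T0 before 24 months.** A subject last seen event-free at 6 months is imputed a 12-month outcome with the chance of an event by 24 months. That is too high for any cumulative first-event endpoint.
- **T0 after 24 months.** A subject known to be event-free at 24 months can never become a 24-month event. X is 0 for that state, the posterior is Beta(1, 1+Y) with mean 1/(2+Y), and almost no later events are imputed. Subjects last seen earlier receive only their 24-month risk. The incidence comes out too low.

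The state list is also incomplete for the later years. Only the 24-month set is added, so the text does not say whether known status at 3 or 4 years is used for a 4- or 5-year prediction.

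At stake are the descriptive incidences and credible intervals for MACCE, MAE, stroke, death, rehospitalization and pacemaker implantation. Two competent programmers could obtain different figures from the same data. The error would also vary between reports, because it depends on how many subjects are imputed.

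**Working it through.** **Reproducing the plan's figures.** I rebuilt the E/P/N chain from Table 8 with the common logit shift described in C.7.4.

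- With no shift, the 24-month rates are 18.7% (TAVI) and 20.7% (SAVR), as C.7.4 states.
- For a TAVI target of 0.20 the shift is 0.07012 (stated 0.07012076). The transitions match Table 14, for example P(E24|N6) = 0.1372 and P(E24|N12) = 0.0963.
- On the C.7.3 expected accrual, 576 subjects enter in months 1-21, then 45 a month. Subject 1400 enters at 21 + (1400 − 576)/45 = 39.3 months, so the Early Win falls at 51.3 months.
- By then 1400 subjects have reached 12 months and 860 have reached 24 months. With dropout uniform to 6%, 1400 × 0.97 = 1358 and 860 × 0.94 = 808, as in Tables 6 and 7.

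**Per imputed subject, from Table 14.**

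- T0 = 12, last seen N at 6 months: 0.1372 is used where P(E12|N6) = 0.0428 applies, a ratio of 3.2.
- T0 = 18, last seen N at 12 months: 0.0963 is used where P(E18|N12) = 0.0428 applies, a ratio of 2.2.
- At a 17% TAVI rate the first pair becomes 0.116 against 0.036.

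**Incidence at the Early Win, T0 before 24 months.** Averaged over the last-seen states, the literal rule gives each subject without T0 data the 24-month risk. With n0 of 1600 subjects followed to T0:

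literal rate = [n0 × π(T0) + (1600 − n0) × 0.17] / 1600

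The chain at a 17% 24-month rate in each arm gives π(12) = 0.0946 (TAVI) and 0.1028 (SAVR), and π(18) = 0.1290 and 0.1334. The results below use unrounded inputs.

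| T0 | n0 | Arm | Rule at T0 | Literal rule | Excess (points) |
|---|---|---|---|---|---|
| 12 months | 1400 | TAVI | 9.46% | 10.40% | 0.94 |
| 12 months | 1400 | SAVR | 10.28% | 11.12% | 0.84 |
| 18 months | 1130 | TAVI | 12.90% | 14.10% | 1.20 |
| 18 months | 1130 | SAVR | 13.34% | 14.41% | 1.08 |

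For example, TAVI at 12 months is (1400 × 0.0946 + 200 × 0.17)/1600 = 0.1040. Counting the 42 dropouts as unobserved too (n0 = 1358) gives 10.6% for TAVI and 11.3% for SAVR.

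For 24-month rates of 12% to 22% and all three accrual rates, the excess is 0.6 to 1.2 points at 12 months and 0.6 to 1.8 points at 18 months.

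**Effect on the comparison.** The TAVI−SAVR difference moves by 0.94 − 0.84 = 0.10 point at 12 months and 1.20 − 1.08 = 0.12 point at 18 months.

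**T0 = 36 months at the Early Win.** About 356 of 1600 subjects have 36 months of follow-up, before dropout. The documents give no hazard after month 24, so I assume h per 6 months. The TAVI rate under the rule at T0 is 1 − 0.83 × (1 − h)². The literal rule gives (356 × that rate + 1244 × 0.17)/1600.

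| Assumed h | Rule at T0 | Literal rule | Shortfall (points) |
|---|---|---|---|
| 2% | 20.3% | 17.7% | 2.6 |
| 4% | 23.5% | 18.4% | 5.1 |
| 5% | 25.1% | 18.8% | 6.3 |

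**Where little changes.** At expected accrual the last subject has 7.6 months of follow-up at the Early Win, so 30-day and 6-month rates move only through loss to follow-up. At the final analysis the same holds for 12 and 18 months. With 3% lost by month 12 (C.7.1), the TAVI effect is about 0.03 × (0.17 − 0.0946) = 0.002, or 0.2 point.

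**T0 reached by nobody.** At the Early Win about 15 subjects have reached 4 years and none 5 years. Even with the rule restated at T0, X = Y = 0 leaves Beta(1,1), whose mean event probability is 1/2 for every unresolved subject.

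**The case against.** The strongest reply is that this is a drafting carry-over and not a biased method. C.11.3 models itself on the primary analysis and works through the case T0 = 24 months. The 24-month and 2-year sentences can be read as continuing that example. Elsewhere the section imputes E subjects at T0 and draws inference from values at T0. The extra 24-month states for a later T0 have a purpose only if the target is T0. This largely stands: the intended reading is visible, and an analyst who follows it avoids the bias. It does not remove the point, because the only sentence defining the transition model says something else and nothing in the section resolves the conflict.

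It is also fair that one extra set of states is right for the 3-year example given. For 4 and 5 years, however, the section names no further visits.

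A reader might infer that every incidence other than the 24-month one would be wrong, or that a labeling claim is exposed. The documents support neither. Rates at 30 days and 6 months barely move. The primary endpoint has its own rule in C.5 with a true 24-month target. The binary tests in C.12.1 (objectives 13-18) use the comparison of proportions without predictions.

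**Conclusion.** C.11.3 contradicts itself, and its prediction rule gives wrong results at time points other than 24 months if followed as written. The material cases are limited:

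- 12 and 18 months at the Early Win: cumulative incidence too high by about 1 point in each arm.
- 3 to 5 years reported before follow-up is complete: incidence too low, by about 2.6 to 6.3 points at 3 years over the assumed hazard range.

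The between-arm difference at 12 and 18 months moves by only about 0.1 point when the 24-month rates are equal.

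These sizes rest on the primary-endpoint skeleton as a stand-in for endpoints with other timing, on the expected accrual profile, and, at 36 months, on a hazard the documents do not supply and on no dropout. The direction holds for cumulative first-event endpoints. It is not assured for a state that can reverse, such as presence of atrial fibrillation (C.10, item 19). The point warrants correction for clear, reproducible reporting and does not threaten the trial's main conclusions.

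**What to change.** In C.11.3:

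1. Replace 24 months, 24-month and 2-year with T0 in the updating, prediction and posterior sentences, so that X and Y count subjects in that state whose status at T0 is known. The worked example for T0 = 24 months can stay if labeled as such.
2. State that the interim states are all scheduled visits before T0. This adds 3 years for T0 = 4 years, and 3 and 4 years for T0 = 5 years.
3. Give no predicted rate at a T0 that no subject has reached, since the Beta(1,1) prior alone would then drive the imputation.

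The cost is a few words in the SAP and a T0 parameter in the program. No data collection, sample size or primary analysis changes. The one practical consequence is that a yearly rate cannot be predicted until some subjects have reached that year.

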### C.4.1 Hypothesis of non-inferiority

The primary objective is to establish that TAVI is non-inferior to SAVR for the primary endpoint. The hypothesis of interest is:

$$H_A: \pi_T < \pi_C + \delta$$

where  $\pi_T$  and  $\pi_C$  denote binary rates of all-cause mortality or disabling stroke during a fixed follow-up of 24 months for the treatment (TAVI) and control (SAVR) groups, and  $\delta = 0.07$ . This study is designed using Bayesian statistical techniques. TAVI will be declared to be non-inferior to SAVR if it can be established that the posterior probability  $\Pr(H_{A, \delta=0.07} | \text{data}) > \Psi$ , where  $\Psi$  is a pre-specified threshold value. If, in addition, it can be shown that  $\Pr(H_A: \pi_T < \pi_C + 0 | \text{data}) > \Psi_{\text{SUP}}$ , TAVI will be declared to be superior to SAVR. The values chosen for  $\Psi$  and  $\Psi_{\text{SUP}}$  are described below.

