## C.5 Predictions

Outcomes at 24-month are binary and are denoted "E" (for having experienced an Event) or "N" (for not having experienced an event). Predicted values of 24-month outcomes for those subjects who have not yet yielded 24-month outcomes will be based on intermediate outcomes observed at 1 month, 6 months, 12 months, and 18 months. These intermediate outcomes are:

[figure not shown]
- "E" -- subject has had a known primary event (death or disabling stroke) at the time point in question
- "P" -- subject is known to have had a "possible primary event" at the time point in question. "Possible primary events" are adverse events that may later be determined to be Disabling Strokes. This determination takes 90 days, by definition. For example, a subject may have a stroke at month 5 which cannot be known to be a Disabling Stroke until Month 8. At Month 6, such a subject is in the "P" state.
- "N" -- subject has not had a primary event or a "possible primary event" at the time point in question.

Subjects without 24-month outcome data will thus be considered to be in one of 26 states (13 for each treatment group). The 13 states are:

- no interim data
- E or P or N at 1 month, no subsequent data
- E or P or N at 6 months, no subsequent data
- E or P or N at 12 months, no subsequent data
- E or P or N at 18 months, no subsequent data

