12. Change in EQ-5D from baseline to 3 months: TAVI vs. SAVR (secondary objective #11). The hypothesis of interest is

$$H: \mu_{TAVI} > \mu_{SAVR}$$

where  $\mu_{TAVI}$  and  $\mu_{SAVR}$  denote the mean improvements in the EQ-5D from baseline to 3 months. The objective will be evaluated using a Bayesian version of a two-sample t-test (see Section C.11). The posterior probability  $P(H | \text{data})$  will be calculated and compared to a threshold of 0.975.

13. Incidence of MACCE at 30 days or hospital discharge, whichever is longer: TAVI vs. SAVR (secondary objective #1). The hypothesis of interest is

$$H: \pi_{TAVI} < \pi_{SAVR}$$

where  $\pi_{TAVI}$  and  $\pi_{SAVR}$  denote the binary rate of MACCE at 30 days or hospital discharge (if longer). The posterior probability  $P(H | \text{data})$  will be calculated and compared to a threshold

of 0.975. The statistical method will be the Bayesian version of a comparison of proportions (see Section C.11).

14. Incidence of major vascular complication at 30 days or hospital discharge, whichever is longer: TAVI vs. SAVR (secondary objective #3). The hypothesis of interest is

$$H: \pi_{TAVI} < \pi_{SAVR}$$

where  $\pi_{TAVI}$  and  $\pi_{SAVR}$  denote the binary rate of major vascular complications at 30 days or hospital discharge (if longer). The posterior probability  $P(H | \text{data})$  will be calculated and compared to a threshold of 0.975. The statistical method will be the Bayesian version of a comparison of proportions (see Section C.11).

15. Incidence of major or life-threatening bleeding events at 30 days or hospital discharge, whichever is longer: TAVI vs. SAVR (secondary objective #3). The hypothesis of interest is

$$H: \pi_{TAVI} < \pi_{SAVR}$$

where  $\pi_{TAVI}$  and  $\pi_{SAVR}$  denote the binary rate of major or life-threatening bleeding events at 30 days or hospital discharge (if longer). The posterior probability  $P(H | \text{data})$  will be calculated and compared to a threshold of 0.975. The statistical method will be the Bayesian version of a comparison of proportions (see Section C.11).

16. Incidence of all strokes at 30 days or hospital discharge, whichever is longer: TAVI vs. SAVR (secondary objective #15). The hypothesis of interest is

$$H: \pi_{TAVI} < \pi_{SAVR}$$

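### C.11.3 defines the probability of superiority with the inequality reversed: for event endpoints it gives the probability that TAVI has the higher event rate

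*Combined protocol and SAP*

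**What the plan says.** The SAP based on CIP Version 12.0 describes in C.11.3 how dichotomous secondary endpoints are compared when some subjects have not reached the time point of interest. Its first principle is: "The modeling is analogous to the predictions in the Primary Objective". Subjects are placed in states E, P or N. Those in E are carried forward as E, and for the others the plan models the probability of becoming E. Observed and predicted outcomes are combined, and "a posterior probability of non-inferiority (or superiority) is calculated". The rule is then given: "The probability of superiority is then estimated by the proportion of these stored values wherein" p_t > p_c. The same inequality stands in C.11.3 of the SAP based on CIP Version 4.0.

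The meaning of the symbols comes from the sections that C.11.3 is modelled on. In C.5, state E is defined as "subject has had a known primary event (death or disabling stroke) at the time point in question". In C.4.1 the two rates are "for the treatment (TAVI) and control (SAVR) groups". C.4.1 also fixes the direction: "TAVI will be declared to be superior to SAVR" when the posterior probability that π_T is below π_C exceeds Ψ_SUP.

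**The concern.** Superiority of TAVI on an adverse event means fewer events on TAVI. C.11.3 counts the draws with more. Someone programming from the text would report, under the label of superiority, the probability of the opposite.

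The outputs concerned are much of the comparative safety record: MACCE, its components, MAE, deaths, strokes and rehospitalization, most of them at eight time points from 30 days to 5 years. A reader shown a probability of superiority of 0.99 for stroke would draw the reverse of what the data say. A programmer who silently turned the sign round would depart from the written rule, and section C of the SAP asks for deviations to be described and justified in the Final Report.

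**Working it through.** No figure in the SAP depends on this rule, so there is none to reproduce. The check has three parts.

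**1. What p_t and p_c measure.** C.11.3 models the probability of becoming E, and E is having had the event. So p_t is the TAVI event proportion, p_c is the SAVR event proportion, and p_t > p_c means more events on TAVI.

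**2. Whether any endpoint makes the written direction right.** The two-arm endpoints in C.10 assigned to the comparison with predictions are:

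- #1 MACCE (time-point series), #2 its components, #3 MAE
- #5 clinical efficacy, which despite its name is a composite of death, stroke, hospitalization, NYHA class III or IV and valve dysfunction
- #6 time-related safety, also a composite of bad outcomes
- #7 conduction disturbance requiring a pacemaker
- #13 valve-related hospitalization
- #14 cardiovascular and valve-related death
- #15 strokes and TIAs
- #19 atrial fibrillation

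A higher rate is unfavourable for all of them. #22, prosthetic valve dysfunction, also uses the method, but for TAVI alone, so no comparison arises.

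Direction elsewhere in the same SAP:

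| Section | Direction stated |
|---|---|
| C.4.1, C.4.2.2 (primary superiority) | π_T < π_C |
| C.11.1 (same comparison, no predictions) | p_t − p_c < δ; p_t/p_c < θ |
| C.12.1 #13 to #17 (binary label claims) | π_TAVI < π_SAVR |
| C.11.3 | p_t > p_c |

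**3. Size.** For continuous posteriors, Pr(p_t > p_c) = 1 − Pr(p_t < p_c), so the written value is exactly one minus the intended one.

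Inputs for an illustration: 1600 mITT subjects at 1:1 (C.4.2), so 800 per arm; SAVR rate 17% (C.4.2.1), or 136 events; Beta(1,1) priors (C.11.3). The TAVI rates are assumed. With full data the posteriors are Beta(1+Y, 1+800−Y). Both inequalities were evaluated on the same 400,000 draws.

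A second run added a simplified prediction step. Table 6 gives 808 subjects with 24-month outcomes at the Early Win look under expected accrual, so 404 per arm were taken as observed and 396 as known only to month 12. The share of events occurring by month 12 was assumed to be 56%; Table 14 of Appendix G.3 gives 0.1125/0.2000 = 0.5625. The transition from N at 12 months used a Beta(1+X, 1+Y) posterior, with 100,000 draws.

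| TAVI vs SAVR observed | As written, full data | p_t < p_c, full data | As written, with prediction | p_t < p_c, with prediction |
|---|---|---|---|---|
| 12% vs 17% | 0.002 | 0.998 | 0.008 | 0.992 |
| 14.5% vs 17% | 0.085 | 0.915 | 0.121 | 0.879 |
| 17% vs 17% | 0.500 | 0.500 | 0.499 | 0.501 |
| 22% vs 17% | 0.994 | 0.006 | 0.978 | 0.022 |

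A normal approximation confirms the first row. The posterior means are 97/802 = 0.1209 and 137/802 = 0.1708, a difference of −0.0499. The standard deviation is √[(0.1209 × 0.8791 + 0.1708 × 0.8292)/803] = 0.0176. Then z = −2.84 and Pr(p_t > p_c) is about 0.002.

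**The case against.** The best defence is that nothing decisive rests on the sentence, and most of that defence stands.

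- Primary superiority has its own rule in C.4.1 and C.4.2.2, in the right direction, and its predictions come from C.5.
- The binary label-claim objectives #13 to #17 in C.12.1 each state π_TAVI < π_SAVR, and #18 states π_TAVI < 30%. All six use the comparison without predictions, which is C.11.1.
- C.12 says that the remaining secondary objectives will not support labeling claims, and C.10 gives the affected endpoints no superiority threshold.
- Arm-level incidences and the credible interval for p_t − p_c do not use the inequality. A value of 0.01 beside a lower TAVI rate and an interval below zero would look odd at once.

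A reader might therefore infer too much: that an arm with more strokes or deaths would be declared superior, or that a claim-bearing test such as MACCE at 30 days or discharge is reversed. The documents do not support either. No rule turns the C.11.3 probability into a declaration, and objective #13 shows the correct sign. Nor do the documents show that the program carries the error, since they contain no code.

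It can also be said that the intended sign is recoverable. C.11.1 calls its counts successes, and C.8 speaks of a composite success while modelling E and N outcomes, so this may be success-oriented wording carried into an event setting. That explains the slip but does not remove it. C.11.3 models E, no two-arm endpoint assigned to it is one where more is better, and it is the only section that defines this probability for these endpoints. C.9.2 plans inferential statistics for most of them, so a mislabelled number could be reported.

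**Conclusion.** The inequality in C.11.3 is wrong as written for every two-arm endpoint that uses it. The reported quantity would be the posterior probability that TAVI has the higher event rate, exactly one minus the intended value (0.002 in place of 0.998 in the 12% versus 17% illustration).

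The error is confined to superiority probabilities for the secondary endpoints analysed with predictions that lie outside the label-claim hierarchy. It changes no success criterion, threshold, sample size or simulated type I error rate.

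The conclusion rests on reading p_t and p_c as event proportions, which the state model in C.11.3 requires. The numerical examples rest on assumed TAVI rates and, with prediction, on a simplified state structure in which every subject without a 24-month outcome has 12-month status. The direction of the error depends on neither.

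**What to change.** In C.11.3, replace p_t > p_c with p_t < p_c (or p_t/p_c < 1 on the ratio scale), and state that for event endpoints superiority of TAVI means the lower proportion. One such sentence covers every endpoint routed to the method; a direction label beside each C.10 entry is optional. Then check that the analysis program uses that direction for these outputs.

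The cost is one line of SAP text and a program check. No simulation has to be rerun, and there is no statistical downside.
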